Study Methodology Overview: The proposed RCT aims to examine the efficacy of a PFI for reducing PSM misuse. Study 1 will document normative perceptions on each of the 3 participating campuses. Study 2 will examine the efficacy of a web-delivered PFI adapted and expanded from models like BASICS which will contain tailored information on normative misperceptions of PSM misuse, contrasting commonly held misconceptions about the benefits of PSM with research-based information about the actual effects of PSM, and learning and study strategies as alternatives to PSM misuse compared to a control condition, as well as components targeting comorbid alcohol and marijuana misuse. For Study 3, an in-person individually-delivered PFI (adapted from web format to face-to-face) addressing PSM and AOD misuse will be compared to the web-delivered PFI tested in Study 2 and to an assessment only control. The two studies will evaluate outcomes with respect to both short-term (6 months) and longer-term (12 and 18 months) reductions in four substance-related outcomes: (a) the perceived norms and benefits of PSM misuse, (b) PSM misuse frequency, (c) marijuana use frequency, and (d) alcohol use frequency and quantity.

Setting: Participants will be recruited from three universities: The University of Washington (UW), the University of Maryland College Park (UMCP), and University at Albany, State University of New York (UAlbany). UW is located in Seattle, WA and UMCP is located nine miles from Washington DC, with each school's total undergraduate enrollment of more than 30,000. UAlbany, which is one of four SUNY University Centers, is classified as a Research II and NCAA Division I institution with more than 12,000 undergraduate students. All three universities are coeducational and very diverse with regard to race, ethnicity, religion, gender, age, disability, and sexual orientation.

Studies 1 & 2 Recruitment Procedures: A total of 8,172 undergraduates for Study 1 and 15,732 for Study 2 aged 18 to 24 (age restricted in order to maintain comparability with prior SBI/PFI interventions with college students) will be randomly selected from the University Registrars' databases across the 3 sites. Students will be emailed an invitation to log on to a secure web browser, read a consent statement and indicate their willingness to participate in the study. Approximately 50% of invited students will respond to the invitation (Study 1 N=4,086 and Study 2 N=7,866).

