Aim 1: To examine whether perceived norms of PSM differs from the “actual” prevalence as estimated by the screening sample, the actual prevalence will be subtracted from the perceived prevalence. A one-sample t-test will be used to assess whether the difference score is statistically significantly greater than 0. If the difference score is a non-normal distribution, we will instead use a non-parametric Wilcoxon sign rank test.

Aim 2: Evaluate efficacy of interventions. We will first examine effects of the intervention on perceived norms, benefits of PSM, and use of alternative strategies as separate outcomes using linear mixed models (a.k.a. hierarchical linear or multilevel models¹²⁰). This project will have 5 repeated measures, yielding up to 6,000 Level 1 observations (repeated-measures) across 1,200 Level 2 (people). The following equation represents a basic analytic model for Aims 2 and 3:

$$\text{Level 1: } Y_{ti} = \pi_{0i} + \pi_{1i}(\text{Post})_i + \pi_{2i}(\text{Month6})_i + \pi_{3i}(\text{Month12})_i + \pi_{4i}(\text{Month18})_i$$

$$\text{Level 2: } \pi_{0i} = \beta_{00} + \beta_{01}(\text{Tx})_i + \beta_{02}(\text{Site})_i + r_{00i}$$

$$\pi_{1i} = \beta_{10} + \beta_{11}(\text{Tx})_i + \beta_{12}(\text{Site})_i$$

$$\pi_{2i} = \beta_{20} + \beta_{21}(\text{Tx})_i + \beta_{22}(\text{Site})_i$$

$$\pi_{3i} = \beta_{30} + \beta_{31}(\text{Tx})_i + \beta_{32}(\text{Site})_i$$

$$\pi_{4i} = \beta_{40} + \beta_{41}(\text{Tx})_i + \beta_{42}(\text{Site})_i$$

where *Post*, *Month6*, *Month12*, and *Month18* are dummy codes for follow-up visit such that the reference time point is baseline; *Tx* represents randomly assigned treatment condition; *Site* represents the study site; *i* indexes participants; *r_{00i}* represents a random effect for the intercept; and *Y_{ti}* represents the outcome for each individual, *i*, at each time, *t*. $\beta_{11} - \beta_{41}$ are primary coefficients as they compare treatment conditions for the difference in the outcomes from baseline to each of the follow-up visits. The model assumes conditional independence, given random-effects and (multivariate) normality of Level 2 random-effects. As additional analyses, we will also specify time as a continuous variable in order to assess differences between intervention and control groups in slopes over time.

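### The Aim 1 one-sample t-test treats a sample-estimated prevalence as a known constant, so its standard error omits that estimate's sampling error; the Wilcoxon fallback omits it too and tests a different quantity

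*Combined protocol and SAP*

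**What the plan says.** The analysis is set out under (c) Approach, Data Analysis, Evaluation of Specific Aims, Aim 1. The comparison value is described as "prevalence as estimated by the screening sample", and "the actual prevalence will be subtracted from the perceived prevalence". The test is then: "A one-sample t-test will be used to assess whether the difference score is statistically significantly greater than 0". The fallback reads: "If the difference score is a non-normal distribution, we will instead use a non-parametric Wilcoxon sign rank test". No criterion for non-normality is given.

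No standard error, confidence interval, alpha or power is stated for Aim 1. The bootstrap later in Data Analysis is for mediation only.

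The section on recruitment for Studies 1 and 2 expects about half of 8,172 and of 15,732 invited students to respond, giving 4,086 for Study 1 and 7,866 for Study 2. The section on screening for eligibility gives Study 1 a single survey, open to every selected student, that covers both own misuse and normative perceptions. Only Study 2 has a screening questionnaire. The Aim 1 text does not say which of these samples supplies the prevalence.

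**The concern.** A one-sample test is right when the comparison value is known. Here it is an estimate. Taking the same number away from every score changes the mean but not the spread, so the test sees only the variation in perceptions. A proportion estimated from 0/100 responses has a per-person SD of 36 points at 15% prevalence, which may exceed the SD of the perceptions themselves. The omitted term is therefore not negligible beside the retained one.

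The fallback raises a second problem. Signed-rank tests a median-type centre and assumes symmetry, whereas a prevalence is a mean. Under skew, which is one way the switch would be triggered, the two tests can disagree. At about 4,000 respondents a test on the mean does not need normal scores.

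At stake is the precision of the estimated gap between perceived and actual norms, pooled and by campus, and the error rate of the test if a gap is small.

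**Working it through.** **Inputs from the documents.** Study 1 n = 8,172 × 0.50 = 4,086. Study 2 screening m = 15,732 × 0.50 = 7,866. Both match the stated figures. The pilot yes/no item (Preliminary/Pilot Studies, item 4) gives 74% perceived and 25% actual.

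**Assumptions.** The documents give no SD of perceived prevalence (SD_W), no size for the correlation r between perceived norm and own use, and no response scale for the Study 1 item. I assume a percentage scale, SD_W of 15 to 30 points and prevalence p of 5% to 25%. Own misuse is scored 0/100, so SD_Y = 100√(p(1−p)).

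**Formulas.**
- Planned: SE = SD_W/√n.
- Same respondents: SE = √(SD_W² + SD_Y² − 2r·SD_W·SD_Y)/√n.
- Separate sample: SE = √(SD_W²/n + SD_Y²/m).

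**Central example: SD_W = 25, p = 15%, SD_Y = 35.7, √n = 63.9.**
- Planned: 25/63.9 = 0.39 points.
- Same respondents, r = 0: √(625 + 1,275)/63.9 = 43.6/63.9 = 0.68 (ratio 1.74).
- Same respondents, r = 0.2: √(1,900 − 357)/63.9 = 39.3/63.9 = 0.61 (ratio 1.57).
- With a true gap of zero, a nominal one-sided 5% test rejects with probability 1 − Φ(1.645/ratio), which is 15% to 17%. A nominal 95% interval built from the planned SE would cover 74% to 79%.

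**Range.**
- Separate sample of 7,866: the ratio runs from 1.13 (SD_W 30, p 5%) to 2.31 (SD_W 15, p 25%). It always exceeds 1.
- Same respondents, r from 0 to 0.2: from 1.11 to 3.06. The top value needs SD_W 15, p 25% and r = 0.
- Same respondents, break-even: the planned SE stops being too small once r exceeds SD_Y/(2·SD_W). The lowest threshold on the grid is 21.8/60 = 0.36 (SD_W 30, p 5%). In the central example it is 35.7/50 = 0.71.

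**Yes/no item at the pilot margins.** SD_W = 43.9 and SD_Y = 43.3. The ratio is 1.41 at r = 0 and 1.14 at r = 0.34, the largest correlation those margins allow.

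**Effect on the conclusion.** At the pilot gap of 49 points, z is 49/0.686 = 71 as planned and 49/0.964 = 51 with the full SE at r = 0. In the central example, one-sided significance needs a gap of 1.645 × 0.39 = 0.64 points as planned, against 1.01 to 1.12 points with the full SE. Only gaps in that narrow band would change side. The 95% half-width goes from 0.8 to 1.2–1.3 points pooled. With 1,362 per campus (equal thirds assumed), it goes from 1.3 to 2.1–2.3.

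**Simulation at n = 4,086** (beta-distributed, right-skewed perceptions, no true mean gap). The planned one-sided 5% test rejected in 15% to 20% of 3,000 datasets per setting. A one-sample test on perceived minus own misuse rejected in 4% to 6%. The one-sided Wilcoxon rejected in 0% of 300. In one example with mean excess +3.3 points and median excess −6.0 points, the t-test gave p < 10⁻¹⁸ and Wilcoxon p = 0.30.

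**The case against.** The strongest reply is that nothing turns on this. The documents cite contrasts of 74% against 25%, 89% against 19% and 71.4% against 9.2%. Some of these are shares of students holding a belief or reporting misuse among peers, not mean estimates of prevalence, but they point to gaps far beyond one or two points. The inflated error rate arises only where the true gap is near zero. This stands.

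A reader might infer that the plan's published error bars are wrong. The plan states none for Aim 1, so the criticism reaches the test and any interval later derived from it.

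A reader might also infer that the normative feedback is compromised. The feedback description under Prescription Stimulant Medication Misuse PFI shows perceived and actual use as values, with no standard error. The efficacy models for Studies 2 and 3 do not use this quantity either.

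Nor is the planned SE too small in every case. The protocol expects perceived norms to relate to own use, and with one sample a high enough correlation removes the understatement. The percentage scale is also an assumption: the one perceived-use item worded in the documents is yes/no, and there the ratio is modest.

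Finally, the fallback is not shown to inflate error. In the skewed null simulation it was conservative. The objection to it is that it answers a different question.

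What the reply does not remove is the omission itself. Nothing in Data Analysis carries the prevalence's sampling error into the test.

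**Conclusion.** The point holds as a correctable flaw in the Aim 1 method. The SE treats an estimated prevalence as known. With a separate sample of 7,866 it is always too small, by about 1.1 to 2.3 fold for SD_W of 15 to 30 points and prevalence of 5% to 25%. With the same respondents it is too small unless the norm-use correlation exceeds SD_Y/(2·SD_W), which is about 0.36 or higher over that grid. The central example is 0.39 planned against 0.61 to 0.68. For a yes/no item like the pilot's, the ratio is about 1.1 to 1.4. All of these sizes rest on assumed SDs and correlations.

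The Wilcoxon switch shares the omission, changes the quantity tested and is not needed at this sample size.

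The documents do not support the stronger reading that the Aim 1 finding would be spurious. At gaps of the size they cite, direction and significance are unchanged. The consequence is overstated precision of the gap and, where a gap is as small as about one point, an unreliable test. The point estimates used in the feedback and the Study 2 and 3 analyses are unaffected.

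**What to change.** 1. State which sample supplies the actual prevalence: the Study 1 survey respondents or the Study 2 screening respondents. The correct SE depends on the answer.
2. If it is the same respondents, define each student's score as perceived prevalence minus own misuse (0 or 100) and keep the ordinary one-sample t-test. The mean gap is the same and the SE is then correct.
3. If it is a separate sample, use the two-source SE shown above, or a bootstrap that resamples both sources.
4. Delete the normality-triggered switch to Wilcoxon.
5. Apply the same method pooled and per campus.

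The cost is a few sentences of SAP text and, in most settings, a somewhat larger SE. No new data are needed.

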use brief interventions whose primary target will be PSM misuse; however there is evidence that these types of interventions will have secondary effects/reductions on other substance use¹⁶⁶. Thus, our approach is significant as it has the potential to be both efficacious and highly efficient for reducing PSM misuse and related comorbid alcohol and marijuana use in a high-risk population (i.e., college students).

Evidence for Brief Interventions with College Students. The proposed intervention builds on the success of existing Brief Motivational Interviewing (MI)¹⁶⁸ strategies such as Brief Alcohol Screening and Intervention for College Students (BASICS)^{5,6}, but adapts the approach to focus on PSM misuse in addition to comorbid alcohol and marijuana misuse. The BASICS program incorporates personalized feedback regarding normative perceptions and actual norms, motives for using, and strategies to minimize negative consequences from alcohol use, and has been deemed by the NIAAA Task Force on College Drinking Prevention as a Tier 1 Intervention^{63, 64}. Several theories underlie BASICS, including Social Comparison⁶⁵ and Social Learning Theory⁶⁶ which suggest people compare themselves to others as a way to evaluate appropriateness of their own behavior and learn by watching others. While BASICS targets alcohol use, other substances have been the focus of in-person feedback-based interventions patterned after BASICS. For example, an in-person, personalized feedback intervention (PFI) for marijuana designed and evaluated by members of our team showed reductions in number of joints used and a trend toward fewer consequences compared to controls¹⁶⁹. Thus, adapting PFIs to address PSM misuse is timely and fills a critical need.

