Participants will complete a battery of web-based follow-up assessments at 6, 12, and 18 months post-baseline for which they will receive \$20, \$25, and \$30, respectively. Participants will additionally complete a brief post-intervention assessment of satisfaction with services and convenience of the intervention, and at each assessment they will be asked whether they have sought other drug treatment since the intervention to control for possible confounding treatment effects. These data will help determine the ideal interventions for the service delivery settings in regard to ease of access and utilization by participants.

Study 3 Training and Ongoing Supervision of Interventionist: One potential method for maintaining or enhancing the efficacy of individual brief interventions for college students seeking campus health and mental health care beyond the life of a research project is to train and supervise existing service providers to deliver the feedback interviews. The current approach will provide training to enhance existing knowledge of the UAlbany Counseling and Health Center staff regarding PSM misuse, and will utilize an existing provider imbedded in the Counseling Center staff at UAlbany to provide the in-person interventions. The provider will complete specific additional training related to both the MI process and PSM, alcohol, and marijuana content of the proposed intervention, and will participate in weekly supervision meetings with Drs. [name] and [name]. In addition, all intervention sessions will be audio-recorded and reviewed for adherence to the protocol and MI competence using existing protocols developed for use in prior funded projects at UAlbany and UW. The interventionist will also complete an adherence checklist after each individual session, to indicate which components were covered in each intervention session. Scores on adherence/competence measures and checklists will be reviewed and included as a covariate in secondary analyses of intervention efficacy.

Measurement and Assessment Procedures: Measures will be completed via a secure web survey, using DatStat Illume and will last 30-45 minutes. Measures selected are in Appendix A.

PSM Measures		
PSM Use	DV	
 PSM Timeline Followback (TLFB) - Quantity and past-30-day frequency of PSM misuse¹⁸⁸ Medical Use, Medical Misuse, and Non-Medical Use Questionnaire^{23, 80}

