We will then examine effects on PSM, marijuana, and alcohol use and consequences. These outcomes are integers, bounded at zero, and often times positively skewed. Because of potential violations of regression assumptions that can arise due to the non-normal distribution, we will use a generalized form of the linear mixed model (GLMM) with a Poisson distribution in order to more appropriately model these outcomes as counts¹¹⁷. Count regression coefficients are connected to the outcome via a natural log link and are commonly exponentiated (e^β) to yield rate ratios (RRs) describing the proportional increase in the outcome for a 1-unit increase in the predictor (e.g., Treatment (1) compared to Control (0)).

To assess mediation hypotheses, we will utilize an approach that has been used by co-investigators with similar data to the proposed study¹⁹⁷. Kenny et al.¹⁹⁸ described mediation using multilevel models for longitudinal treatment data similar to the present data. Specifically, Kenny et al. focused on change in the direct treatment pathways from a model without the mediator to a model with the mediator (i.e., the common c and c' pathways in the mediation literature). In the present context, that is the treatment cross-level interactions with time ($\beta_{11} - \beta_{41}$) for the model presented above compared to one in which mediators are included as Level 1 time-varying covariates. We will use this approach and consider the percent reduction in effects after the mediator is included in the model. In Neighbors et al¹⁹⁹, this approach was extended using a nonparametric bootstrap¹⁹⁹ to allow estimation of the indirect path without making normality assumptions on the sampling distribution of the indirect effect. Perceived benefits and norms of PSM, use of alternative strategies, and alcohol and marijuana use will be included as the Level 1 time-varying mediators of interest and PSM use and consequences will be modeled as the outcomes. To assess moderators of efficacy, we will include level 2 covariates for baseline levels of motivations of PSM and demographic characteristics as well as their interactions with treatment in the GLMM.

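### Every treatment-by-visit coefficient is called primary, but no PSM instrument, visit, test or multiplicity rule is named as deciding efficacy, and one of those coefficients has no scheduled Study 2 outcome data

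*Combined protocol and SAP*

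**What the plan says.** - **What is primary.** Data Analysis, Aim 2, sets out a basic model for Aims 2 and 3 with dummies for Post and months 6, 12 and 18. It says that the treatment-by-visit terms, β11 to β41, "are primary coefficients as they compare treatment conditions for the difference in the outcomes from baseline to each of the follow-up visits". No visit is ranked. A slope model is secondary to this: "As additional analyses, we will also specify time as a continuous variable".
- **Outcomes.** The same model is used first for norms, benefits and alternative strategies, and then: "We will then examine effects on PSM, marijuana, and alcohol use and consequences". The Significance section gives the ranking: the team will "use brief interventions whose primary target will be PSM misuse", and the Study 2 hypotheses treat alcohol and marijuana as secondary effects and norms, benefits and alternatives as mediators. The Power section is based on PSM use.
- **Instruments.** The measures table lists two instruments for PSM use as dependent variables. One is the "PSM Timeline Followback (TLFB) - Quantity and past-30-day frequency of PSM misuse"; the other is a questionnaire on medical use, medical misuse and non-medical use. Neither is marked as leading.
- **Alpha.** A 5% level appears only in the power simulation, for each hypothesis singly. Aim 3 compares web and in-person delivery each with control and with each other, with no adjustment stated.
- **Visits.** Aim 2 says: "This project will have 5 repeated measures, yielding up to 6,000 Level 1 observations (repeated-measures) across 1,200 Level 2 (people". Study 2 Baseline and Randomization schedules follow-up at 6, 12 and 18 months only. For Study 3: "Participants will additionally complete a brief post-intervention assessment of satisfaction with services and convenience of the intervention".
- **Model.** "The model assumes conditional independence, given random-effects and (multivariate) normality of Level 2 random-effects". The only random effect is an intercept, the count models are Poisson, and the intercept equation includes a treatment term, β01.

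**The concern.** A reader of the final report could not tell in advance which result settles efficacy. Suppose the intervention shows a significant reduction at 6 months and not at 12 or 18, or on the Timeline Followback and not on the questionnaire. The plan supports calling that a success and equally supports calling it mixed. If each visit is a separate question, each keeps its own 5% level, but the plan does not say so. If one significant visit is enough, the error rate exceeds 5%.

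Study 3 has the same gap across three comparisons. Its hypothesis stresses 18 months only for in-person versus web, so the deciding visit may differ by comparison.

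Two features of the model bear on whether any chosen test keeps its level. One coefficient called primary (Post) has no scheduled Study 2 outcome. The Poisson model also has no term for extra variation within a person, although the protocol describes misuse as episodic, clustered around mid-terms and finals.

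**Working it through.** **1. The plan's own power figures.** Study 2: 600 per arm, coefficient -.13, power above .80. Study 3: 100 per arm, coefficient -.3, power .80 or higher. The simulation's intercept and random-intercept variance are not given, so these cannot be reproduced exactly. A consistency check is possible. In the stated model with complete data and equal visit means, the variance of one coefficient is the sum of 1/(n × mean) over four arm-by-visit cells. Power .80 needs SE = .13/2.80 = .0464, which corresponds to a mean of about 3.2 per visit: (3 + e^.13)/(600 × .0464²). The same step for Study 3 gives 3.8. These means are only working assumptions. The plan says above .80, from 200 data sets (Monte Carlo SE = √(.8 × .2/200) = .028), and true power of .745 to .95 would give Study 2 means of 2.8 to 5.3. The stated power is plausible and is taken as given below.

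**2. Error if any significant visit counts.** Each coefficient is a follow-up arm difference minus the same baseline arm difference. With equal variances the correlation between visits is .5; two arms sharing a control also correlate .5. Each test is two-sided at 5% (sidedness is not stated). Normal draws give:

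| One PSM measure | Two-sided error | False benefit (nominal 2.5%) |
|---|---|---|
| Study 2, three visits | 12.5% | 6.3% |
| Study 2, four visits | 15.6% | 7.8% |
| Study 3, two control comparisons, three visits | 22% | 11% |

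**3. Visit count.** 5 × 1,200 = 6,000 is the plan's figure. The Study 2 schedule gives 4 × 1,200 = 4,800. The post-intervention assessment described for Study 3 covers satisfaction and convenience, not PSM misuse.

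**4. Candidate Study 2 tests.** Take an effect that one coefficient detects with power .80, so its expected z is 2.80.
- *Average of three visits.* Its variance relative to one coefficient is (1 + 1/3)/2 = .667. For a constant effect, z = 2.80/√.667 = 3.43 and power is .93. For an effect at 18 months only, z = (2.80/3)/√.667 = 1.14 and power is .21.
- *3-df joint test.* The noncentrality is 2.80² × 1.5 = 11.8 in both cases, and power is .83 in both.

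**5. Study 3 under Holm.** Holm's power lies between Bonferroni and unadjusted testing. For a coefficient of -.3 at one visit that is between .66 (alpha .05/3) and .80. If web has half the in-person effect, the in-person versus web contrast at one visit has .29 unadjusted and .16 under Bonferroni.

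**6. Standard errors.** Null simulations of the Study 2 average added visit-level variation within person (log-SD 0, .3, .5; assumed). With β01 dropped (600 per arm, mean 3.2, intercept SD 1), rejection with model-based SEs was 5.1%, 12.8% and 25.3%; with robust SEs it was 5.2%, 5.0% and 5.3%. A second simulation that kept β01 gave 4.8%, 14.9% and 29.1% model-based, and 5.0%, 5.1% and 5.4% robust. In the first set-up, robust power for a constant -.13 was .97 at log-SD 0 and .60 at .5.

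**7. Baseline arm term.** Baseline is completed before randomisation in both studies, so a common baseline mean is justified. At an assumed mean of 3.2 and intercept SD of .5, 1.0 and 1.5, dropping β01 lowers the variance of one coefficient by 27%, 11% and 4%.

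**The case against.** The strongest reply is that the plan gives more direction than the label primary suggests. That sentence identifies which model parameters carry the treatment effect; it does not declare a set of co-primary endpoints. A reader might multiply visits by every outcome put through the model and conclude that the plan has dozens of primary tests. The documents do not support that, because they rank PSM misuse first, alcohol and marijuana as secondary effects, and the beliefs and alternatives as mediators. This part of the reply stands. What remains open is the instrument, visit and test for PSM misuse.

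It can also be said that testing each question at 5% is the natural reading, since the power statement refers to a given hypothesis and the methodology overview separates short-term (6 months) from longer-term (12 and 18 months) outcomes. That is fair, and it is why the error rates are conditional on an assumption. Half of each two-sided rate is also apparent harm rather than benefit. Even so, per-question testing does not say which question decides.

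Averaging over visits is not dictated by the Study 2 hypothesis, and it performs poorly if the effect appears late. That is accepted, so the joint test is offered as an equal alternative. Nor does the emphasis on 18 months for in-person versus web restrict that comparison to 18 months.

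Finally, the amounts of extra-Poisson variation have no source in the documents. They show sensitivity and are not a forecast. The case for robust standard errors rests on the model's missing overdispersion term and the protocol's own account of episodic use.

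**Conclusion.** The concern holds for PSM misuse. The plan names no deciding instrument, visit, test or alpha rule, and no multiplicity procedure for the three Study 3 comparisons. The error rates in step 2 apply only if any significant visit is taken as an effect, and they assume correlations of .5. The Post term and the 6,000 observations conflict with the Study 2 schedule whatever is assumed, so β11 has no scheduled Study 2 outcome data.

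Two further inferences should be resisted. A reader might conclude that the trial is underpowered. The stated power is for one coefficient at the 5% level and is not shown to be wrong; naming a single test need not reduce it in Study 2. A reader might also take β01 as a source of bias. The contrast is unbiased with it, and only some precision is lost, by an amount that depends on means and random-intercept SDs that the documents do not give.

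This should be settled before analysis. It does not undermine the design.

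**What to change.** Before analysis, amend the SAP as follows.

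1. Name one primary measure of PSM misuse frequency, for example the past-30-day Timeline Followback frequency.
2. Study 2: name one primary test over the 6-, 12- and 18-month coefficients, either their average or the 3-df joint test. The choice depends on whether a sustained or a late effect is expected. Report single visits, other outcomes and the slope model as secondary.
3. Study 3: state the visit or combination of visits for each comparison, put the two control comparisons and in-person versus web under one procedure such as Holm, and restate power under it.
4. Correct the Post term and the five-measure, 6,000-observation figure to match the schedule, or state which outcome is collected at Post.
5. Use participant-clustered robust standard errors for the Poisson models.
6. Optionally, drop β01 (both arm terms in Study 3).

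The cost is SAP wording and model code, with no new data. The average gives up most of its power against an effect confined to one visit, while the joint test gives up some against a constant effect. Holm lowers Study 3 power per comparison. Robust standard errors lower the reported power if counts vary beyond Poisson within a person, but that lower figure is the honest one.
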